LVEF	left ventricular ejection fraction
m	meter
MBC	metastatic breast cancer

Abbreviation	Term
MedDRA	Medical Dictionary for Regulatory Activities
mg	milligram
mmHg	millimeters of mercury
MUGA	multiple-gated acquisition scan
ORR	objective response rate
OS	overall survival
PD	progressive disease
PFS	progression-free survival
PK	pharmacokinetics
PR	partial response
PT	preferred term
QoL	Quality of Life
RECIST	Response Evaluation Criteria in Solid Tumors
SAE	serious adverse event
SAP	Statistical Analysis Plan
SD	stable disease
SOC	System Organ Class
std	standard deviation
TEAE	treatment-emergent adverse event
WHODrug	World Health Organization Drug Reference List

1. PURPOSE OF THE ANALYSES

This statistical analysis plan (SAP) provides a comprehensive and detailed description of strategy and statistical methodology to be used for analysis of data for the PUMA-NER-1301 study. This study is sponsored by Puma Biotechnology, Inc.

The purpose of the SAP is to ensure the credibility of the study findings by pre-specifying the statistical approaches to the analysis of study data prior to data base lock. This analysis plan is meant to supplement the study protocol. Any deviations from this plan will be described in the Clinical Study Report (CSR).

2. PROTOCOL SUMMARY

2.1. Study Objectives

2.1.1. Primary Objective

The co-primary objectives of this study are

- to compare independently adjudicated progression free survival (PFS) following treatment with neratinib plus capecitabine versus lapatinib plus capecitabine in patients with HER2-positive (HER2+) metastatic breast cancer (MBC) who have received two or more prior HER2 directed regimens in the metastatic setting.
- to compare overall survival (OS) following treatment with neratinib plus capecitabine versus lapatinib plus capecitabine in this population.

2.1.2. Secondary Objectives

The secondary objectives of this study are:

- Investigator assessed PFS.
- Objective response rate (ORR), duration of response (DOR) and clinical benefit rate (CBR) (complete response [CR] or partial response [PR] or stable disease [SD] ≥ 24 weeks).
- Time to intervention for symptomatic metastatic central nervous system (CNS) disease.
- Safety (adverse events [AEs] and serious adverse events [SAEs]).
- Health outcomes assessment.

2.1.3. Exploratory Objective

The exploratory objective of this study is to assess the population pharmacokinetics (PK) of neratinib when administered in combination with capecitabine.

2.2. Overall Study Design and Plan

This is a randomized, multi-center, multinational, open-label active-controlled, parallel design study of the combination of neratinib plus capecitabine versus the combination of lapatinib plus capecitabine in HER2+MBC patients, who have received two or more prior HER2-directed regimens in the metastatic setting. Patients will be randomized in a 1:1 ratio to either the neratinib plus capecitabine or lapatinib plus capecitabine arms.

Following a 21-day screening period, eligible patients will be randomized to Arm A or Arm B. Baseline assessments will be performed prior to randomization and Cycle 1/Day 1 dosing. Patients will then participate in the active treatment phase, consisting of 21-day treatment cycles. Patients are anticipated to participate in the study for an average of 28 months. This includes approximately 0.5 months for screening, an estimated average of 9.5 months for treatment, and

an estimated average of 18 months for the long-term follow-up phase. Patients who permanently discontinue treatment will enter the long-term follow-up phase until death or withdrawal of consent.

2.3. Study Population

The study population will include all patients that sign and date an approved informed consent form and are eligible per the criteria defined in the protocol. A full list of the inclusion and exclusion criteria can be found in the PUMA-NER-1301 protocol.

2.4. Treatment Regimens

Patients in the Neratinib + Capecitabine Combination arm will receive medication as described below:

- Neratinib: six 40 mg tablets (total daily dose 240 mg) orally, once daily with food, preferably in the morning, continuously.
- Capecitabine: 150 mg or 500 mg tablets (total dose of 1500 mg/m² daily in 2 evenly divided doses), orally with water within 30 minutes after a meal. Dose taken daily for Days 1 to 14 of a 21-day cycle.

Patients in the Lapatinib + Capecitabine Combination arm will receive medication as described below:

- Lapatinib: five 250 mg tablets (total dose 1250 mg) orally, once daily, 1 hour before or after breakfast, continuously.
- Capecitabine: 150 mg or 500 mg tablets (total dose of 2000 mg/m² daily, in 2 evenly divided doses), orally with water within 30 minutes after a meal. Dose taken daily for Days 1 to 14 of a 21-day cycle.

2.5. Treatment Group Assignments or Randomization

Patients will be randomized in a 1:1 ratio to one of the following treatment arms:

- Arm A: neratinib (240 mg) + capecitabine (1,500 mg/m² daily, 750 mg/m² BID)
- Arm B: lapatinib (1250 mg) + capecitabine (2,000 mg/m² daily, 1000 mg/m² BID)

Patient randomization will be stratified according to:

- Number of previous HER2 directed regimens in the metastatic setting (N= 2 or N ≥3).
- Geographic region (North America vs. Europe including Russia and Israel vs. Rest of the World)
- Visceral vs. Non-Visceral only disease
- Estrogen receptor+ (ER+) and/or progesterone receptor (PR+) (i.e., hormone receptor +) versus ER- and PR- (i.e., hormone receptor -).

2.6. Sample Size Determination

The co-primary endpoints will be analyzed using an overall Type I error rate of 0.01 for PFS and 0.04 for OS. To detect a hazard ratio (experimental vs. control) of 0.70 with approximately 85% power, 419 PFS events (PD/Deaths) are required to be observed; this assumes a median (ITT) PFS of 8.0 months (34.7 weeks) for the experimental arm (neratinib plus capecitabine) and 5.6 months (24.3 weeks) for the control arm (lapatinib plus capecitabine).

It is expected that the 419th event will be observed at approximately 26 months after the first subject is enrolled, which would correspond to approximately half of the death events needed to be observed. At this time, an interim analysis on OS will also be performed. For the OS endpoint, a group sequential method will be employed to maintain the overall Type I error rate at 0.04. Specifically, Lan DeMets alpha spending function approximating the O’Brian-Fleming boundaries will be calculated to create appropriate critical values to which the log rank statistic will be compared (De Mets and Gordon Lan, 1994). If 50% of the deaths are observed at the interim OS analysis, the boundary using the Lan-DeMets alpha spending function is shown in Table 1 for OS interim analysis.

Table 1: Spending Function

Information Fraction	Expected Death Events	Study Month	Boundary (Reject H_0)	2-Sided Significance Level*
50%	185	26	3.066	0.002
100%	378	50	2.058	0.039

* This significance level relates to the 0.04 alpha allocation to OS but will be updated if the entire 0.05 can be allocated to OS.

These boundaries are designed to detect a hazard ratio (experimental vs. control) of 0.725 with approximately 85% power. Overall, 378 OS events (deaths) are required to be observed; this assumes a median (intent to treat [ITT]) OS of 30.3 months for the experimental arm (neratinib plus capecitabine) and 22.0 months for the control arm (lapatinib plus capecitabine).

Approximately 600 subjects will be enrolled and randomized equally between the two treatment arms. This sample size assumes a 1% drop out rate per 12 months (52 weeks) equally distributed between the treatment arms for the PFS endpoint.

3. GENERAL ANALYSIS AND REPORTING CONVENTIONS

All study variables will be listed. Selected variables will be summarized and, when appropriate, analyzed. Data summaries will be presented by treatment group and, when appropriate, visit.

For all safety and efficacy variables, the number of patients will be provided overall and by visit, with the exception of adverse events and concomitant medications, which will not be summarized by visit.

Categorical variables will be summarized using counts and percents. Percents will be displayed to 1 place after the decimal point (XX.X), with the exception of 100%, which will be displayed without additional decimal places. Continuous variables will be summarized using number of patients, mean, median, standard deviation, minimum, and maximum.

Mean and median will be reported at 1 more significant digit than the precision of the data; standard deviation will be reported at 2 more significant digits than the precision of the data. Minimum and maximum will be reported to the same level of precision as the original observations. In general, any calculated values, such as those due to unit conversion, will be rounded to the same number of decimal places as the original data. P-values will be reported to 3 decimal places, with values less than 0.001 displayed as '<0.001.'

In general, the baseline value will be considered the last measurement observed prior to taking the first dose of study treatment.

Data will be listed by treatment and patient. In general, listings will be sorted in the order that columns are displayed, starting with the first column on the left (treatment).

SAS statistical software, version 9.1 or later, will be used for all analyses.

If departures from these general conventions are present in the specific evaluations section of this SAP, then those conventions will take precedence over these general conventions.

4. ANALYSIS POPULATIONS

Four analysis populations will be used for this study: the Intent to treat (ITT) population, the Safety Population, the Pharmacokinetics (PK) population and the Quality of Life population (QoL).

The analysis of the primary and secondary efficacy endpoints will be performed using the ITT population. All safety analyses will be performed using the Safety Population. Exploratory Pharmacokinetics analyses will be performed using the PK population. Quality of life analyses will be performed using the QoL population.

4.1. Intent to treat (ITT) Population

The intent to treat population is defined as all patients who are randomized into the study. Patients will be analyzed in the treatment arm to which they were randomly assigned regardless of which treatment they received.

4.2. Safety Population

The safety population is defined as all patients who received at least one dose of investigational product. Patients will be analyzed based on the treatment they had received regardless of the treatment to which they were randomized.

4.3. Pharmacokinetics (PK) Population

The pharmacokinetics population consists of all patients for whom data on concentrations of study treatment is available.

4.4. Quality of Life (QoL) Population

The QoL population consists of all patients in the safety population for whom a baseline and at least one post baseline Health Outcomes Assessment (HOA) are available.

5. STUDY PATIENTS

5.1. Disposition of Patients

The number and percentage of patients entering and completing each phase of the study will be presented, stratified by treatment. Reasons for withdrawal pre- and post-randomization will also be summarized.

5.2. Protocol Deviations

Protocol deviations will be classified and monitored regularly during the duration of the study. Among other reasons, failure to meet any of the protocol inclusion or exclusion criteria will be considered a protocol deviation. All protocol deviations will be listed and summarized by type and treatment group.

6. DEMOGRAPHIC AND OTHER BASELINE CHARACTERISTICS

Descriptive statistics will be provided for all demographic and baseline characteristics based on the ITT population. Demographic data, medical history, concomitant disease, and concomitant medication will be summarized by means of descriptive statistics or frequency tables, overall and stratified by treatment. For categorical variables, the number and percentages of patients in each category will be presented. For continuous variables, summaries will include the number of patients with data, mean, median, standard deviation, minimum, and maximum.

6.1. Demographic and baseline characteristics

The following demographic and baseline variables will be summarized by treatment group:

- age (years)
- age group (<65, ≥ 65 years)
- sex
- race & ethnicity (per CRF)
- region
- height (cm)
- weight (kg)
- body mass index (BMI)

Body mass index (BMI) will be calculated as:

$$\text{BMI (kg/m}^2\text{)} = \text{Weight (kg)} / (\text{Height(cm)} * 0.01)^2$$

6.2. Medical History

Medical history data including: chronic conditions, relevant surgical procedures, symptoms experienced during the previous 30 days, symptoms ongoing at the time of Screening, any

medical conditions that require medication and cancer history will be collected at screening, within 21 days before Cycle 1/ Day1 in accordance with the Schedule of Procedures included in the protocol.

Cancer history variables include date of first diagnosis, nodal status, histology, tumor stage at diagnosis, previous chemotherapy/biotherapy/immunotherapy, previous adjuvant therapy, previous radiation, and prior cancer related surgical therapies.

Medical history and cancer history data will be summarized and listed.

6.3. Prior and Concomitant Medications

Concomitant medications will be defined as medications documented on the Concomitant Medications CRF. Concomitant medications will be coded using the World Health Organization (WHODrug) dictionary and summarized in a table and a data listing.

7. MEASUREMENTS OF TREATMENT COMPLIANCE

Duration of treatment will be summarized separately for each study compound by treatment group. In addition, the cumulative quantity, dose intensity (quantity per time unit), and the relative dose intensity (dose intensity/scheduled dose per time unit) will be summarized.

The number of patients with dose holds or dose reductions will be tabulated for each test article by treatment group.

8. EFFICACY EVALUATION

8.1. Overview of Efficacy Analysis Issues

8.1.1. Handling of Dropouts or Missing Data

Missing assessments for PFS, the number of subjects who drop out prior to PFS or OS, and the length of follow up for dropouts will be summarized by treatment group. Sensitivity analyses will be performed to assess the impact of subject dropout or missing assessments on the primary efficacy analyses.

Other endpoints that could be affected by missing values (e.g. health outcome assessments) will be analyzed using a sensitivity analysis to quantify the impact of missing values in the results.

8.1.2. Multicenter Studies

Data from all sites will be pooled for the purpose of analyses. Exploratory analyses by site are not an objective of this study and are not currently planned.

8.2. Efficacy Variables

Table 2 gives an overview of the efficacy variables and the analysis methods that will be used for analysis.

Table 2: Efficacy Variables and Analysis Methods

Endpoint	Method
Primary	
Progression Free Survival (independently adjudicated)	
 • Kaplan-Meier estimates • Stratified Log-rank test • Stratified Cox Proportional Hazards model
Overall Survival	
 • Kaplan-Meier estimates • Stratified Log-rank test • Stratified Cox Proportional Hazards model
Secondary	
Progression Free Survival (investigator assessed)	
 • Kaplan-Meier estimates • Stratified Log rank test • Stratified Cox Proportional Hazards model
Objective Response Rate (independently adjudicated and investigator assessed)	
 • Cochran-Mantel-Haenszel test (CMH)

Table 2: Efficacy Variables and Analysis Methods (Continued)

Endpoint	Method
Duration of Response (independently adjudicated and investigator assessed)	
 • Kaplan-Meier estimates
Clinical Benefit Rate (independently adjudicated and investigator assessed)	
 • Cochran-Mantel-Haenszel test (CMH)
Time to intervention for symptomatic metastatic central nervous system disease (CNS) (investigator assessed)	
 • Cumulative incidence function for time to intervention for symptomatic CNS
Health Outcome Assessments	
 • Random Effects Mixed Model

These are definitions of the criteria used to determine objective tumor response for target lesions. These components make up the endpoints which are defined below, see the protocol for more detail.

Complete Response (CR): Disappearance of all target and non-target lesions. Any pathological lymph nodes (whether target or non-target) must have reduction in short axis to <10 mm. All lymph nodes must be non-pathological in size (<10 mm short axis).

Partial Response (PR): At least a 30% decrease in the sum of diameters of target lesions, taking as reference the Baseline sum diameters.

Progressive Disease (PD): At least a 20% increase in the sum of diameters of target lesions, taking as reference the smallest sum on study (this includes the Baseline sum if that is the smallest on study). In addition to the relative increase of 20%, the sum must also demonstrate an absolute increase of at least 5 mm. PD can also be determined if there is unequivocal progression of existing non-target lesions. (Note: the appearance of one or more new lesions is also considered progression).

Stable Disease (SD): Neither, sufficient shrinkage to qualify for PR, nor sufficient increase to qualify for PD, taking as reference the smallest sum diameters while on study.

8.2.1. Progression Free Survival (PFS)

Progression free survival (PFS) is defined as the time interval from the date of randomization until the first date on which recurrence, progression (per RECIST v1.1), or death due to any cause, is documented. It is not necessary to confirm disease progression.

All tumor assessments and deaths collected will be used except in the following 2 cases:

1. If a subject misses 2 or more consecutive assessments immediately prior to the documentation of PD or death the subject will be censored at the last assessment prior to the missed visits (following the FDA guidance on clinical trial endpoints for the approval of cancer drugs and biologics).
2. For subjects that started a new anti-cancer therapy, all tumor assessments and deaths after the start date of new anti-cancer therapy will be excluded from the analysis.

After taking into account the two conditions listed above, subjects without documented PD or death, including those who dropped out, will be censored at their last tumor assessment. Patients who did not have any tumor assessments after the screening visit will be censored on the randomization date.

Assessment of PFS will be performed by a blinded, independent, central review of tumor assessments for all patients at Screening, and then after every 6 weeks from first dose of investigational product, regardless of treatment schedule modification (e.g., dose delay), until documented disease progression or death. PFS will be assessed using the Response Evaluation Criteria in Solid Tumors (RECIST v1.1).

8.2.2. Overall Survival (OS)

Overall survival is defined as the time from randomization to death due to any cause, censored at the last date known alive on or prior to the data cutoff employed for the analysis. Patients who switch anticancer therapy will continue to be followed for the OS assessment.

Survival data will be collected throughout the study treatment phase and during post-progression follow-up. Survival follow-up after patient discontinuation of investigational product will be conducted approximately 4 weeks after treatment discontinuation and then every 12 weeks to assess for survival until subject's loss to follow-up or death.

8.2.3. Central Nervous System Disease (CNS)

Time to intervention for symptomatic metastatic central nervous system disease is defined as the time from randomization to the first start date of an intervention for symptomatic metastatic CNS disease. Subjects that do not have an intervention for symptomatic metastatic CNS and do not die will be censored at the last date known alive on or prior to the data cutoff. Deaths are treated as competing events. Interventions for symptomatic CNS disease will include anti-cancer medication, cancer-related radiation therapy, cancer-related surgery/procedure, or concomitant medication/therapy as collected on the CNS CRF.

8.2.4. Objective Response Rate (ORR)

Objective response rate is defined as the proportion of patients demonstrating an objective response during the study. Objective response includes confirmed complete responses (CR) and partial responses (PR) as defined in the RECIST criteria included in the study protocol. Tumor assessments after the initiation of new anticancer therapy will not be included when determining ORR.

8.2.5. Duration of Response (DOR)

Duration of response is measured from the time at which measurement criteria are first met for CR or PR (whichever status is recorded first) until the first date of recurrence or progressive disease (PD) or death is objectively documented, taking as a reference for PD the smallest measurements recorded since enrollment, per RECIST v1.1. This value is censored at the last valid tumor assessment if PD or death has not been documented. Tumor assessments after the initiation of new anticancer therapy will not be included when determining DOR.

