8 EFFICACY AND SAFETY ASSESSMENTS

8.1 Efficacy Assessment

8.1.1 Clinical Endpoints and Definitions

There are 2 co-primary endpoints in this study: independently-adjudicated PFS and OS. All patients randomized will be evaluated.

The secondary efficacy endpoints include Investigator-assessed PFS, ORR, DOR, and CBR (CR, PR or SD \geq 24 weeks), time to intervention for symptomatic metastatic CNS disease, and health outcomes assessments.

Progression-free Survival

Progression-free survival is determined programmatically from adjudicated PD, defined as the interval from the date of randomization until the first date on which recurrence, progression (per RECIST v1.1 [[Appendix 7](#)]) or death due to any cause, is documented, censored at the last assessable evaluation, or at the initiation of new anticancer therapy. It is not necessary to confirm disease progression.

Overall Survival

Overall survival is defined as the time from randomization to death due to any cause.

Objective Response Rate

The ORR is defined as the proportion of patients demonstrating either a CR or PR per RECIST v1.1 ([Appendix 7](#)) as their best overall response during the study. It is not necessary to confirm response.

Duration of Response

The DOR is measured from the time at which measurement criteria are first met for CR or PR (whichever status is recorded first) until the first date on which recurrence or PD or death is objectively documented, taking as a reference for PD the smallest measurements recorded since enrollment, per RECIST v1.1 ([Appendix 7](#)). The duration of overall complete response is measured from the time measurement criteria are first met for CR until the first date that recurrent disease is objectively documented.

Clinical Benefit Rate

The CBR is defined as the proportion of patients who achieved overall tumor response (CR or PR) or SD for at least 24 weeks. Stable disease is measured from enrollment until the criteria for disease progression or response are met, per RECIST v1.1 ([Appendix 7](#)).

Time to Intervention for Symptomatic CNS Disease

Time to intervention for symptomatic metastatic CNS disease is defined as the date of initiation of intervention or therapy for symptomatic CNS disease determined by the investigator to be due to CNS metastasis. This may include brain, leptomeningeal and epidural metastases including epidural spinal cord compression arising from tumor growth in the epidural space.

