8.3.2. Secondary Efficacy Analyses

The secondary endpoints of ORR, CBR and duration of response will be assessed using the centrally reviewed tumor assessments as well as the investigator tumor assessments. The secondary endpoint of time to intervention for symptomatic CNS disease will only use the investigator-reported data.

The treatment difference in the secondary efficacy endpoint of investigator assessed PFS will be assessed with the product limit estimate of the median time to event. Differences between treatment groups will be examined using a log rank test statistic stratified by hormone receptor status, number of prior HER2-directed regimen in the metastatic setting, visceral disease status, and geographic region strata (similar to the analyses for the primary endpoints). All time-to-event endpoints including time to intervention for symptomatic CNS disease will be displayed using a Kaplan-Meier survival plot.

For the secondary endpoints of ORR and CBR the subjects included in the analyses are those that had measurable disease (per RECIST v1.1) at screening. Any tumor assessments after the start of new anti-cancer therapy will not be included in the analyses for these two endpoints. The treatment difference in the secondary efficacy endpoints of ORR and CBR will be analyzed using a Cochran-Mantel-Haenzel (CMH) Chi-square test, stratified on hormone receptor status, number of prior HER2-directed regimens in the metastatic setting, geographic region and disease category (visceral vs. non-visceral only).

Duration of response will be summarized by treatment group for the patients that responded. If there are patients that continue to respond, they will be censored at their last tumor assessment and a Kaplan-Meier analysis will be done to estimate the duration of response.

With the exception of the CNS endpoint, which will be tested only after the null hypothesis is rejected for OS; all other secondary endpoints are descriptive analyses and will be done at the time of the primary PFS analysis.

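### SAP 8.2.5 removes scans but not deaths after new anti-cancer therapy, so whether a switching responder is censored in the DOR analysis depends on later survival

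*SAP*

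**What the plan says.** For DOR, SAP 8.2.5 runs the clock from first response "until the first date of recurrence or progressive disease (PD) or death is objectively documented". On censoring it says: "This value is censored at the last valid tumor assessment if PD or death has not been documented". On new treatment it says: "Tumor assessments after the initiation of new anticancer therapy will not be included when determining DOR". SAP 8.3.2 adds only this: "If there are patients that continue to respond, they will be censored at their last tumor assessment".

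For PFS, SAP 8.2.1 goes further on both counts. After a switch, "all tumor assessments and deaths after the start date of new anti-cancer therapy will be excluded from the analysis". It also has a rule for gaps in follow-up: "If a subject misses 2 or more consecutive assessments immediately prior to the documentation of PD or death the subject will be censored". The censoring date is then that of the final scan preceding the gap.

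Deaths after a switch will be in the database, because SAP 8.2.2 states: "Patients who switch anticancer therapy will continue to be followed for the OS assessment".

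Protocol 8.1.1 defines DOR as running "until the first date on which recurrence or PD or death is objectively documented". It gives no rule for new therapy or missed scans there, although its PFS definition does censor at new anti-cancer therapy.

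**The concern.** SAP 8.2.5 contains half of a switch rule. Once a responder starts another therapy, later scans cannot contribute a progression, but a later death still can. The patient's record is then decided by something that happens after the switch. A death before the cut gives an event at the date of death. Survival to the cut gives censoring at the last scan before the switch. The Kaplan-Meier estimator assumes that censoring carries no information about the outcome, and here it does.

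The route to this case is open. The trial is open-label, and treatment after discontinuation is left to the investigator (Protocol 10.3). DOR is reported by central review as well as by investigator (SAP 8.3.2). An investigator-called progression that central review does not confirm, followed by a switch, is exactly such a record.

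At stake is the meaning of the reported DOR curve, which would mix time in response with survival on the next therapy, and its consistency with PFS. The planned table of DOR censoring (SAP section 12) also needs one unambiguous rule.

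**Working it through.** The plan states no figure for DOR, so there is none to reproduce. The check has three parts.

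**1. Rules side by side**

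| Situation | PFS (SAP 8.2.1) | DOR (SAP 8.2.5, 8.3.2) |
|---|---|---|
| Scan after new therapy | excluded | excluded |
| Death after new therapy | excluded | not excluded; death is an event |
| Progression or death after 2+ missed assessments | censored before the gap | no rule; counts |

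Nothing carries the PFS rules over to DOR. The supplemental SAP, section 3.3.2, does carry them over, but for the CNS endpoints only. In the 8.2.5 censoring sentence, the word valid qualifies scans, not deaths. The SAP never states outright that post-switch deaths count. That follows because death is an event, censoring requires that no death be documented, and only scans are removed.

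**2. One hypothetical patient** (months from randomization): response at 2, last pre-switch scan at 5, no progression.
- PFS: censored at 5, whatever follows.
- DOR if the patient dies at 20: event at 20 − 2 = 18 months.
- DOR if alive at the cut: censored at 5 − 2 = 3 months.

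With the PFS cut expected about 26 months after first enrolment, a death at month 20 can be seen only in patients randomized in roughly the first 26 − 20 = 6 months. Shorter versions of the case are available to more patients.

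**3. Size, by simulation on assumed inputs.** Time to progression is exponential with rate λ = ln 2 / median DOR. The switching rate is λq/(1 − q), so that a share q switches before progression. Post-switch survival is exponential. Each data set was analysed under the PFS rule and under 8.2.5 as written.

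The first run used a median DOR of 8 months, post-switch median survival of 22 months, 6 to 24 months of follow-up from response and a 6-week scan grid:

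| q | Responders who become post-switch death events | 18-month DOR, PFS rule | 18-month DOR, as written | Change (points) |
|---|---|---|---|---|
| 5% | 1.0% | 0.194 | 0.191 | −0.3 |
| 10% | 2.0% | 0.193 | 0.186 | −0.7 |
| 20% | 4.3% | 0.190 | 0.173 | −1.7 |
| 30% | 7.0% | 0.187 | 0.159 | −2.8 |

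With 120 responders per arm, 10–30% switching gives 0.020 × 120 = 2.4 to 0.070 × 120 = 8.4 such events. The median stayed at 8.29 months, because it can fall only on a scan date.

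The second set of runs matched follow-up to the PFS cut and varied post-switch median survival from 15 to 22 months, with 120 responders and 10–30% switching. It gave about 2–9 events per arm, a fall of about 1–5 points at 18 months, and a fall in the median of about 0.05–0.4 months.

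The direction depends on the cut. At the PFS cut, switchers who die early become events while longer survivors are removed at their last scan, which pulls the curve down. With follow-up to about 50 months most switchers have died, many of them late, and the 18-month estimate rises by about 0.5–2.6 points. The missed-assessment gap was not simulated.

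**The case against.** The strongest reply is that counting a later death is what the protocol says. Protocol 8.1.1 includes death in DOR without a new-therapy exclusion, and it already treats PFS and DOR differently. This stands. A reader might infer that DOR as planned no longer measures what the protocol defines. The documents do not support that, since it is the SAP's scan exclusion, and the remedy below even more so, that adds to the protocol definition. The defect is that scans are removed and deaths are kept.

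A reader might also infer that DOR would be lengthened by late deaths. SAP 8.3.2 schedules DOR at the primary PFS analysis, and SAP 8.3.1 plans a descriptive repeat at the OS analysis for PFS only. At the planned cut the shift is downward. The rise belongs to an update that the SAP does not plan.

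Nor does the SAP predict the switching rate. The 10% in SAP 8.3.1.1 is a trigger for a PFS sensitivity analysis in all patients, not an estimate for responders.

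Impact is limited. SAP 8.3 makes DOR descriptive with no alpha, and SAP Table 2 lists only Kaplan-Meier estimates for it. (Protocol 12.3.2.1 mentions a log-rank comparison, also without alpha.) A censoring table will show who was censored. With 120 responders, the standard error of an 18-month estimate near 0.2 is at least √(0.2 × 0.8 / 120) = 0.037, or 3.7 points, which is similar to or larger than most of the shifts. All of this stands, but none of it makes the rule coherent.

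**Conclusion.** The point holds as an inconsistency in the DOR rule. As written, SAP 8.2.5 makes the censoring of switching responders depend on whether they later die, and it allows DOR to exceed PFS in the same patient. It also lacks the missed-assessment rule used for PFS.

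The expected size is modest: about 2–9 responders per arm at the planned analysis, about 1–5 points off the 18-month estimate, and little or no change in the median (up to about 0.4 months). These figures rest on an assumed responder count, DOR median, switching share and post-switch survival, none of which the documents give. No between-arm effect was computed. Unequal switching could produce one, but its size and direction cannot be judged from the documents. The primary endpoints and the tested CNS endpoint are untouched.

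**What to change.** State in SAP 8.2.5 that both exceptions in 8.2.1 (two or more consecutive missed assessments, and new anti-cancer therapy) apply to DOR, for tumor assessments and for deaths, with censoring at the last assessment before the gap or before the new therapy. Record in SAP section 11 that this adds a censoring rule to the DOR definition in Protocol 8.1.1. If the sponsor prefers a different rule, 8.2.5 should state and justify it, and treat scans and deaths after a switch coherently.

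The cost is one sentence in 8.2.5 and an entry in section 11. The PFS event and censoring flags can be reused. The downside is that a few deaths no longer count as DOR events. The choice should be fixed before results are seen.
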